9.1 Reference Safety Information

The reference safety information (RSI) for PATHWAYS Trial is comprised of the SmPCs for Decapeptyl SR (long-acting formulation of Triptorelin) 22.5mg, Decapeptyl® SR (long-acting formulation of Triptorelin) 11.25mg, Prostap 3 DCS (Leuprorelin Acetate) 11.25mg, and Gonapeptyl (Triptorelin) 3.75mg. Specifically, the tables of 'general tolerance in children' are to be referred to for assessment of expectedness.

9.2 Evaluating AEs and SAEs

Assessment of intensity

The PI or SI will assess intensity for each AE and SAE reported during the study. The assessment will be based on the PI/SI's clinical judgement. The intensity of each AE and SAE recorded in the eCRF should be assigned to one of the following categories:

- **Mild**; An event that is easily tolerated by the participant, causing minimal discomfort and not interfering with everyday activities
- **Moderate**; An event that is sufficiently discomforting to interfere with normal everyday activities
- **Severe**; An event, which is incapacitating and prevents normal everyday activities

The electronic version of this document is the latest version. It is responsibility of the individual to ensure that any paper material is the current version. Printed material is uncontrolled documentation.

An AE that is assessed as severe should not be confused with an SAE. Severity is a category utilised for rating the intensity of an event; and both AEs and SAEs can be assessed as severe.

Assessment of causality

The Investigator is obligated to assess the relationship between investigational product and the occurrence of each AE/SAE. The Investigator will use clinical judgment to determine the relationship. Alternative causes, such as natural history of the underlying diseases, concomitant therapy, other risk factors, and the temporal relationship of the event to the investigational product will be considered and investigated.

The causal relationship to the study product assessed by the Investigator (or medically qualified delegate) should be assessed using the following classifications:

- **Not Related:** In the Investigator's opinion, there is not a causal relationship between the study product and the AE.
- **Unlikely:** The temporal association between the AE and study product is such that the study product is not likely to have any reasonable association with the AE.
- **Possible:** The AE could have been caused by the study participant's clinical state or the study product.
- **Likely:** The AE follows a reasonable temporal sequence from the time of study product administration, abates upon discontinuation of the study product and cannot be reasonably explained by the known characteristics of the study participant's clinical state.
- **Definitely:** The AE follows a reasonable temporal sequence from the time of study product administration or reappears when study product is reintroduced.

There may be situations when an SAE has occurred, and the Investigator has minimal information to include in the initial report to the Sponsor. However, it is very important that the Investigator always assesses causality for every event prior to transmission of the SAE form to the Sponsor. The Investigator may change his/her opinion of causality considering follow-up information, amending the SAE form accordingly. The causality assessment is one of the criteria used when determining regulatory reporting requirements.

Assessment of expectedness

A reasonable possibility of a relationship conveys that there are facts, evidence and/or arguments to suggest a causal relationship, rather than a relationship that cannot be ruled out.

- **Expected:** An adverse reaction, the nature or severity of which is consistent with the applicable Reference Safety Information in the Summary of Product Characteristics for an approved medicinal product

The electronic version of this document is the latest version. It is responsibility of the individual to ensure that any paper material is the current version. Printed material is uncontrolled documentation.

- **Unexpected:** An adverse reaction, the nature or severity of which is not consistent with information in the relevant source document

Follow-up of AEs and SAEs

After the initial AE/SAE report, the Investigator is required to proactively follow each participant and provide further information to the Sponsor on the participant's condition. All AEs and SAEs documented at a previous visit/contact and are designated as ongoing, will be reviewed at subsequent visits/contacts. All AEs and SAEs will be followed until resolution, until the condition stabilises, until the event is otherwise explained, or until the participant is lost to follow-up. Once resolved, the adverse event log will be updated. The Investigator will ensure that follow-up includes any supplemental investigations as may be indicated to elucidate the nature and/or causality of the AE or SAE. This may include additional laboratory tests or investigations, histopathological examinations, or consultation with other health care professionals. New or updated information will be recorded on the originally completed SAE form, with all changes signed and dated by the Investigator. The updated SAE form should be resent to the Sponsor.

Post-study AEs and SAEs

A post-study AE/SAE is defined as any event that occurs outside the AE/SAE detection period. Investigators are not obligated to actively seek AEs or SAEs in former study participants. However, if the Investigator learns of any SAE, including death, at any time after a participant has been discharged from the study, and he/she considers the event reasonably related to the investigational product, the Investigator will promptly notify the Sponsor.

9.3 Adverse event processing responsibilities

The sponsor has delegated the delivery of the Sponsor's responsibility for Pharmacovigilance (as defined in Regulation 5 of the Medicines for Human Use (Clinical Trials) Regulations 2004) to the King's Health Partners Clinical Trials Office (KHP-CTO).

KHP-CTO will report SUSARs to the Research Ethics Committee (REC) and Medicines and Healthcare products Regulatory Agency (MHRA). Reporting timelines are as follows:

- SUSARs which are fatal or life-threatening must be reported no later than 7 days after the sponsor is first aware of the reaction. Any additional relevant information must be reported within a further 8 days;
- SUSARs that are not fatal or life-threatening must be reported within 15 days of the sponsor first becoming aware of the reaction.

The CI and KHP-CTO (on behalf of the co-sponsors) will submit a Development Safety Update Report (DSUR) relating to this trial IMP, to the MHRA and REC annually.

The electronic version of this document is the latest version. It is responsibility of the individual to ensure that any paper material is the current version. Printed material is uncontrolled documentation.

The Trial Statistician will report relevant adverse events to the Data Monitoring Committee. Data on non-serious, severe ARs will be captured where causality is assessed as possible, likely, or definitely, and will be included in DMC reports.

10 Toxicity Management

Monitoring and Management of Adverse Events:

Regular Follow-Up: Participants will attend regular follow-up appointments to assess the efficacy and safety of the treatment. These appointments will include monitoring hormone levels, physical development assessments, routine blood tests, DEXA scans, and physical assessments (height, weight, BMI, blood pressure, and puberty staging).

Psychosocial Screening: Psychosocial screening to identify any unmet needs and escalate these to appropriate services.

Adverse Event Reporting: All adverse events will be recorded in the participants' medical notes, study source data worksheets, and the eCRF. Serious adverse events (SAEs) will be reported within 24 hours to the King's Health Partners Clinical Trials Office (KHP-CTO).

Management of Common Side Effects: Common side effects such as depression, altered mood, anxiety, and hot flushes will be monitored and managed according to clinical guidelines.

Management of Rare Side Effects: Rare side effects such as anaphylactic reactions, haemorrhage, and idiopathic intracranial hypertension will be monitored closely, and treatment will be discontinued if severe cutaneous adverse reactions (SCARs) occur.

Follow-Up of Adverse Events: All adverse events will be followed until resolution, stabilisation, or until the participant is lost to follow-up. Supplemental investigations may be conducted to elucidate the nature and causality of the adverse events.

11 Premature Termination of Trial

The trial may be prematurely discontinued by the Sponsor, Chief Investigator or Regulatory Authority on the basis of new safety information or for other reasons given by the DMEC, PMC, regulatory authority, or ethics committee concerned.

If the trial is prematurely discontinued, active participants will be informed and no further participant data will be collected. The Competent Authority and Research Ethics Committee will be informed within 15 days of the early termination of the trial.

12 Ethics Approval

This protocol and related documents will be submitted for review to Health Research Authority (HRA), REC and MHRA.

PATHWAYS TRIAL, HORIZON INTENSIVE and CONNECT will be conducted in compliance with the principles of the Declaration of Helsinki (1996), the principles of GCP and all of the applicable regulatory requirements (specify current legislation).

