8.6 Treatment Interactions

There are no known drug interactions with Triptorelin or Leuprorelin acetate.

9 Adverse Event Management and Reporting

All adverse events will be recorded in the participant's medical notes, the study source data worksheets and the eCRF. All Adverse Events and Serious Adverse events will be recorded from the signing of the informed consent form until 12 weeks following the final dose. This reporting period reflects the prolonged pharmacological activity of the 6-month Triptorelin formulation. Events suspected to be related to the IMP occurring beyond this window should also be reported.

SAE's will be additionally reported, within 24 hours of site becoming aware of the event, to the KHP-CTO pharmacovigilance team.

All SAEs, SARs and SUSARs (except those specified in this protocol as not requiring reporting) will be reported immediately (and certainly no later than 24hrs) as per the instructions on the SAE report form. SUSARs will be reported prospectively to the chair of the Data Monitoring Committee (DMC); all other safety events will be listed in DMC reports.

The sponsor will report SAEs and/or suspected unexpected serious adverse reactions as required to regulatory authorities, investigators/institutions, and IRBs/IECs in compliance with all reporting requirements according to local regulations and good clinical practice.

The Medicines for Human Use (Clinical Trials) Regulations 2004 and Amended Regulations 2006 gives the following definitions:

- **Adverse Event (AE):** Any untoward medical occurrence in a participant to whom a medicinal product has been administered, including occurrences which are not necessarily caused by or related to that product.

The electronic version of this document is the latest version. It is responsibility of the individual to ensure that any paper material is the current version. Printed material is uncontrolled documentation.

- Adverse Reaction (AR): Any untoward and unintended response in a participant to an investigational medicinal product which is related to any dose administered to that participant.
- Unexpected Adverse Reaction (UAR): An adverse reaction the nature and severity of which is not consistent with the information about the medicinal product in question set out in the SmPC for that product.

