14.2 Programme Steering Committee (PSC)

The PSC will be composed of 7 independent members and additional non-independent members; the independence level will be above 75%. Attendance of non-voting members at PSC meetings will be at the discretion of the chair. The PSC is an executive committee, reporting to the funder, the National Research Collaboration Programme (NRCP), and the trial sponsors.

The PSC is formally appointed by the National Institute for Health and Care Research (NIHR) and members will receive individual letters from the NIHR confirming their role. Independent members will be independent of the Sponsor organisations and of any recruiting study sites.

The PSC will agree the frequency of meetings prior to the start of the trial; however, it is likely the PSC will meet at least bi-annually.

The trial may be prematurely discontinued by the Sponsor, Chief Investigator or Regulatory Authority on the basis of new safety information or for other reasons given by the Data Monitoring Committee / Programme Steering Committee regulatory authority or ethics committee concerned.

If the trial is prematurely discontinued, active participants will be informed, and no further participant data will be collected. The Competent Authority and REC will be informed within 15 days of the early termination of the trial.

The electronic version of this document is the latest version. It is responsibility of the individual to ensure that any paper material is the current version. Printed material is uncontrolled documentation.

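### The early-termination clauses stop all participant data collection and so contradict the protocol's own rules for recording and following adverse events

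*Protocol*

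**What the plan says.** Section 11 of the protocol allows the trial to be ended early "on the basis of new safety information or for other reasons given by the DMEC" and the other bodies it lists. It then states that "active participants will be informed and no further participant data will be collected". Section 14.2 repeats the rule almost word for word: "If the trial is prematurely discontinued, active participants will be informed, and no further participant data will be collected". Neither place makes an exception for safety data.

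The safety sections set their own end points. Under section 9, adverse events and serious adverse events are recorded "from the signing of the informed consent form until 12 weeks following the final dose". The reason given is that the six-month triptorelin formulation stays active for a long time. Section 9 adds that suspected drug-related events after that window should also be reported. Section 9.2 states: "All AEs and SAEs will be followed until resolution, until the condition stabilises", with other explanation or loss to follow-up as the remaining end points. Section 10, in the paragraph directly above section 11, states: "All adverse events will be followed until resolution, stabilisation, or until the participant is lost to follow-up". None of these rules is conditional on the trial still running.

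**The concern.** The two sets of instructions cannot both be followed on the day the trial is stopped. A site with an open adverse event is told by sections 9.2 and 10 to keep following it, and by sections 11 and 14.2 to collect nothing more.

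The conflict matters most in a safety stop. New safety information is the first ground for termination named in both places, so the data rule would take effect just when the course of the suspected harm most needs documenting. What is learned about harm also has a later use: section 4.7 makes the planned post-trial access arrangement depend on the trial not having identified significant harm.

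**Working it through.** The protocol gives no figure to reproduce here. The check is a comparison of text, with one small calculation.

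**The rules side by side, for a participant on the termination date**

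| Situation | Sections 9, 9.2 and 10 | Sections 11 and 14.2 |
|---|---|---|
| New event within 12 weeks of last dose | Record | Collect nothing |
| Event already open | Follow to resolution, stabilisation, other explanation or loss to follow-up | Collect nothing |
| Suspected related event after 12 weeks | Should be reported | Collect nothing |

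All three rows conflict. The protocol gives no order of precedence between these sections.

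**Length of the recording conflict**

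- Input: a recording window of 12 weeks after the final dose (section 9). 12 × 7 = 84 days.
- If termination also ends dosing, the last injection given becomes the final dose. For a participant injected *d* days before the stop, the mandated recording still to run is max(0, 84 − *d*) days.
- *d* = 0 gives 84 days. *d* = 28 gives 56 days. *d* = 84 or more gives 0 days.
- Under section 11 the figure is 0 days in every case.

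So 84 days is the maximum for one participant, not a typical value. As an illustration, assume six-monthly injections (section 5.2.3), six months taken as 26 weeks, and a stop date falling evenly within the injection interval. Then 12 / 26 = 46% of participants on treatment would still be inside the window.

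Follow-up of open events is a separate component with no fixed length. It applies to any participant with an unresolved event, however long ago the last dose was given.

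**Comparison with an individual stop**

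Under section 5.6, a participant who discontinues GnRHa stays in follow-up on the schedule of the randomised arm until the study ends. Sections 4.8 and 4.14.10 point the same way. Read literally, then, stopping the whole trial for safety produces less safety information per participant than one participant stopping alone.

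**The case against.** The strongest reply is that the safety information would not all disappear. Events are also written in medical notes (section 9). An investigator who learns of a related serious event after a participant has left the study must notify the sponsor (section 9.2, post-study events). Reporting of suspected unexpected serious reactions runs from the sponsor's awareness (section 9.3). Registry linkage, where consented to, captures fractures and major health events (section 15.5). The DMC can also recommend a pause of enrolment or dosing while it assesses a signal (section 14.3), and section 11 does not apply to a pause.

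This stands in part. It makes the loss partial, and a reader who inferred that the outcome of any harm would be lost altogether would be going too far. It does not remove the conflict. Section 9.2 says investigators need not actively seek events in former participants, registry linkage is passive and depends on consent, and neither is written as an exception to section 11.

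A second reply is that the clause is generic and means research outcome data only, leaving the pharmacovigilance duties intact. That may have been the intention. The text says participant data without qualification, twice, so the intention needs to be stated.

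Three stronger readings are tempting but not supported:

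- **All 226 participants, each with about six months unobserved.** Six months is the dosing interval. The mandated recording window is 12 weeks. The delayed arm (113 in Table 1) starts GnRHa one year after randomisation, so at many stop dates a good part of that arm would not have been dosed.
- **Continued follow-up of dosed participants would rescue the randomised safety comparison.** In the first year the comparator is the undosed delayed arm, which such follow-up would leave out. After month 12 both arms are scheduled for treatment, and section 2.2 describes the contrast as one of timing and cumulative effect.
- **Scheduled DEXA scans, bloods and examinations must continue.** These come from the section 4 schedule, not section 9. The contradiction does not require them, and they would add visits and cost.

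**Conclusion.** The contradiction is real and stands as written in the protocol. Sections 11 and 14.2 end all participant data collection at early termination. Sections 9, 9.2 and 10 require recording and follow-up to go on, and nothing says which rule governs.

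Taken literally, the cost is up to 84 days of active adverse event recording for a participant dosed just before the stop, less for those dosed earlier, together with active follow-up of every event open on that date. Passive routes would remain. The 84 days assumes that dosing ends with the trial, and that component applies only to participants who have been dosed. The conflict itself does not depend on how many participants that is.

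This is an internal inconsistency in data collection. It has no bearing on sample size or error rates, and it implies no view on when treatment or the trial should be stopped. It should be corrected beforehand, because an actual safety stop is a poor time to settle which section applies.

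**What to change.** Amend the data sentence in sections 11 and 14.2 to say that, after premature termination, adverse event and serious adverse event recording and follow-up continue as sections 9, 9.2 and 10 already require, and that other participant data collection ends. Use the same wording in both places.

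The drafting is about one sentence in each section. In operation, sites would keep the adverse event log and serious-event reporting open for up to 12 weeks after each participant's last dose, and until open events reach one of the end points in section 9.2. That work is already required by the safety sections, so no new assessment is added. If the sponsor also wants some scheduled safety assessments to continue after a stop, that is a separate decision with its own visit and staffing costs.

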12.1 Protocol amendments and version control of study documents

The Trial Manager will be responsible for preparing and submitting protocol amendments to the ethics committee.

The Trial Manager will be responsible for updating the ISRCTN register following relevant protocol amendments.

Subsequent protocol amendments will be submitted to the REC and Regulatory Authorities for approval, and will comply with regulations, particularly specifying, Pharmacovigilance reporting and providing the REC & MHRA with progress reports, and a copy of the Final Study Report.

13 Statistical Methods

13.1 Trial

13.1.1 Primary Outcome

1. The primary outcome for the PATHWAYS TRIAL is the quality of life of children referred to national gender services for young people in the UK, measured using the CYP self-report version of the KIDSCREEN-10 questionnaire.

13.1.2 Secondary Outcomes

13.1.2.1 *Scales of Gender-Related Distress, Mental Health Symptoms and Physical Health measures :*

- a. Utrecht Gender Dysphoria Scale – Gender Spectrum (UGDS-GS)
- b. Revised Children's Anxiety and Depression Scale (RCADS)
- c. Body Image Scale – Gender Spectrum (BIS-GS)
- d. Parental Attitudes of Gender Expansiveness Scale for Youth (PAGES-Y)
- e. SCOFF questionnaire
- f. Sexual attraction questionnaire
- g. ALSPAC measure
- h. Gender identity question
- i. Adolescent Primary Care Traumatic Stress Screen (APCTSS)
- j. KIDSCREEN-52
- k. Height (cm) and weight (kg)

The electronic version of this document is the latest version. It is responsibility of the individual to ensure that any paper material is the current version. Printed material is uncontrolled documentation.

I. Physical health diagnoses

13.1.3 Scales of Suicidal Ideation, Hospitalizations, Mood Symptoms, Behavioural and Functional Difficulties:

- a. Ask Suicide-screening Questions (ASQ)
- b. Child Behaviour Checklist (CBCL)
- c. Youth Self-Report (YSR)
- d. Difficulties in Emotion Regulation Scale – 18 (DERS-18)
- e. Hospitalisations of participants

13.1.4 Experiences of Therapeutic Options:

- a. Rates of referral to, uptake of, and completion of psychological therapy, occupational therapy, speech and language therapy, clinical nursing, youth work support, school/college support, and non-endocrine pharmacological treatments.

13.1.5 Cognitive Assessments

- a) Wechsler Intelligence Scale for Children (WISC-V)
- b) Delis-Kaplan Executive Function System (D-KEFS)
- c) Child and Adolescent Memory Profile (CHAMP)
- d) Memory Validity Profile (MVP)
- e) Behaviour Rating Inventory of Executive Function (BRIEF)

